“Effects of the GLP-1 receptor agonist liraglutide on lower limb perfusion in people with type 2 diabetes and peripheral artery disease: a randomized controlled trial (STARDUST)” is designed to determine the effect of injectable liraglutide on peripheral perfusion in individuals with type 2 diabetes and PAD. Peripheral perfusion will be assessed through the $TcPO_2$ measurement on the foot. Moreover, we will evaluate the effect of GLP-1RAs on parameters of glyco-metabolic control, inflammation, angiogenesis and cardiovascular risk markers. Particularly, we will analyze:

- glyco-metabolic parameters [fasting glucose, glycated hemoglobin (HbA_{1c}), weight, body mass index (BMI), waist circumference, systolic and diastolic blood pressure];
- lipid profile (total cholesterol, LDL cholesterol, HDL cholesterol, triglycerides);
- inflammation markers [C-reactive protein (CRP), fibrinogen, tumor necrosis factor alpha, interleukin-6];
- renal function parameters [creatinine, azotemia, urine albumin to creatinine ratio (UACR), glomerular filtration rate (eGFR)];
- angiogenesis markers [endothelial progenitor cells (EPCs) and vascular endothelial growth factor (VEGF)];
- PAD clinical assessment (ABI, 6-minutes walking test);
- sexual hormones levels and sexual function.

Study design

STARDUST is a single-center, randomized clinical trial lasting 24 weeks. The study will include a screening visit, a randomization visit and 2 follow-up visits (3 month and 6 month).

Study population

Eligibility will be considered for individuals with type 2 diabetes aged > 35 years, PAD diagnosed through doppler ultrasound, angio-CT, angiography in the past 12 months, TcPO₂ value of the foot ranged between 49 and 30 mmHg.

Inclusion criteria

- diagnosis of type 2 diabetes
- HbA_{1c} ranged between 6.5% and 8%
- Glucose-lowering therapy with metformin and/or insulin on stable doses for at least 3 months

Exclusion criteria

- diagnosis of type 1 diabetes
- current or recent treatment with GLP-1RAs and/or DDP-4 inhibitors
- participation to other clinical research, including drug administration
- contraindications to the treatment with GLP-1RAs
- plans for pregnancy or current pregnancy or breast feeding
- history of thyroid disease
- inflammatory bowel disease
- acute coronary and/or cerebravascular disease within the previous 14 days
- plans and/or indications to peripheral revascularization procedure
- estimated glomerular filtration rate (eGFR) below 15 ml/min per 1.73m²

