- previous history or current diagnosis of neoplasms and/or anti-neoplastic therapies within 5 years from randomization
- history of diabetic ketoacidosis
- current therapies with steroids and/or anti-psychotic medications
- any concomitant conditions which can preclude participation in the study

Female participants in fertile age have to use contraceptives during the study. Moreover, women who meet inclusion criteria will be screened for pregnancy before the completion of the enrollment.

Randomization

Randomization using a computer generated random-number sequence.

Allocation

Concealed in sealed study folders that will be held in a central, secured location until after informed consent will be obtained.

Interventions

LIRA GROUP: participants assigned to LIRA group will start on 0.6 mg once daily liraglutide subcutaneous injection at approximately the same time of the day. The dose will be titrated up on a weekly schedule by 0.6 mg increase to a target dose of 1.8 mg or the maximum tolerated. In accordance with standards of medical care, cardiovascular risk factors will be managed as follows:

systolic blood pressure below 130 mmHg and diastolic blood pressure below 80 mmHg obtained, if needed, with ACE inhibitors or angiotensin receptor blockers, LDL-cholesterol below 70 mg/dL, aspirin therapy at the dosage of 100 mg daily or alternatively clopidogrel 75 mg daily in case of documented aspirin allergy.

CONTROL GROUP: individuals assigned to control group will be given, if needed, tailored therapeutic prescriptions to manage blood glucose levels and cardiovascular risk factors, according to the standards of medical care. The established treatment goals for cardiovascular risk factors control will be: systolic blood pressure below 130 mmHg and diastolic blood pressure below 80 mmHg obtained, if needed, with ACE inhibitors or angiotensin receptor blockers, LDL-cholesterol below 70 mg/dL, aspirin therapy at the dosage of 100 mg daily or alternatively clopidogrel 75 mg daily in case of documented aspirin allergy.

Recruitment and time schedule

Recruitment will last 18 months. Participants will be followed up for 24 weeks (6 months).

Time schedule	Visit 1 (Screening)	Visit 2 (Randomization)	Visit 3 (3 months follow- up)	Visit 4 (End of the study)
	Week -1	Week 0	Week 12	Week 24
Informed consent	x			
Eligibility evaluation	x			
Pregnancy screening test [†]	x			
Start of the intervention		x		

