The co-primary outcomes of the study are the peripheral perfusion assessed at baseline and at the end of the study and the proportion of individuals who reaches a 10% increase of the TcPO₂ value from the baseline in each group. The change of TcPO₂ of the foot in people treated with liraglutide compared with individuals of the Control group will be calculated after 6 months. The TcPO₂ change will be evaluated as the difference between TcPO₂ values measured at the end of the trial and baseline.

Secondary outcomes

The secondary outcomes of the study are the change (measured as the difference of variables at the end of the trial vs. baseline) in glyco-metabolic, inflammation and angiogenesis, atherosclerosis

parameters in people treated with liraglutide compared with individuals of the Control group. Moreover, we will evaluate the changes in renal function, sexual hormones levels and sexual function.

18-month extension of the follow-up

An 18-month extension of the follow-up will be performed for all the study population, according to guidelines and good clinical practice. The follow-up will include the glyco-metabolic parameters and the main cardiovascular risk factors, including TcPO₂ assessment.

Data from this extended observation will be collected for additional analyses (mostly regarding the durability of the effects). Individuals who will be lost during follow-up and/or discontinue or modify the glucose-lowering treatment will be excluded from the analyses.

Methods

All individuals will be informed about the aims of the study through a specific information letter. Moreover, during the screening visit, we will collect written informed consent and deliver an information letter for the general practitioner of each participant.

Physical examination - Height and weight will be recorded using the Seca 200 scale, with attached altimeter (Seca, Hamburg, Germany). The WC will be measured in orthostatic position, at anterior-superior iliac spine, using a graduated instrument. BMI will be calculated as weight in kg divided by the height in squared meters (kg/m²). Blood pressure will be measured three times, with patients in sitting position, after at least 15 minutes of rest.

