Descriptive statistics will be used for demographic and baseline clinical characteristics of all participants in the study. Continuous variables will be described as either mean and standard deviation (SD) or medians and interquartile range (IQR) according to sample distribution, and count data will be reported as numbers and percentages. Comparisons of baseline data between groups will be performed by Student's t test or Mann-Whitney Rank Sum test, depending on the normality of sample distribution. Comparison among frequencies was made with the χ^2 test.

To evaluate the change of variables over time Δ values will be calculated as value at the last observation minus value at the start. The paired t test and Wilcoxon signed rank test within each patients' group will be used to assess changes in the studied variables from baseline to the last observation. Two-sample t-test will be used to compare differences between interventions. The χ^2 test will be used for comparing proportions of participants in the 2 groups who reached the primary endpoint after the intervention. Relative Risk (RR) and 95% confidence interval (CI) will be calculated to demonstrate the relationship between the intervention and the achievement of the primary endpoint. Data were also analyzed by analysis of variance for repeated measures with a post-hoc comparisons made with the Scheffé's test. P value < 0.05 will be considered statistically significant. All analyses will be conducted using SPSS version 19.0 (SPSS Inc, Chicago, Ill).

Safety and Adverse Events

Adverse event (AEs) - Any unexpected event occurred in a patient included in a clinical trial after the administration of a pharmacological product. This event is not necessarily related to pharmacological treatment. Therefore, an AE, may be any unpleasant and unwanted clinical sign (for example, an abnormal laboratory finding), symptom, or disease, which is transiently associated with the use of a drug. According to the guidelines of the Common Terminology Criteria for Adverse Events (<https://www.fda.gov/downloads/Guidances/UCM174090.pdf>), AEs will be divided in different grades.

- Grade 1 (mild): lack of symptoms or mild symptoms, with no indication to specific intervention; clinical or diagnostic observation is required.
- Grade 2 (moderate): moderate symptoms requiring local or non-invasive intervention; it may determine a limitation of daily activities.

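### The between-arm test of TcPO2 change makes no use of the week-0 value as a covariate, and the analysis section's definition of change should be aligned with the 6-month outcome definition

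*Protocol*

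**What the plan says.** Primary outcomes defines the TcPO2 change as the difference between "values measured at the end of the trial and baseline", and says that the change with liraglutide "compared with individuals of the Control group will be calculated after 6 months". The visit table schedules TcPO2 at weeks -1, 0, 12 and 24. It places eligibility at week -1, the start of the intervention at week 0 and the end of the study at week 24.

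Planned statistical analysis describes change for all variables together: Δ "values will be calculated as value at the last observation minus value at the start". The within-group tests likewise assess "changes in the studied variables from baseline to the last observation". For the comparison between arms, "Two-sample t-test will be used to compare differences between interventions". The section then adds: "Data were also analyzed by analysis of variance for repeated measures". It names no covariate for any analysis.

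The sample size paragraph gives an SD of 5 mmHg, 10% dropout, at least 50 participants allocated 1:1, 90% power, α of 0.05 and a 10% difference with no mmHg value.

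**The concern.** There are two separate points.

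The first is precision. Subtracting baseline is the same as fixing the slope of week-24 on baseline TcPO2 at 1. If the true slope is lower, the change score keeps variance that the week-0 reading could remove, and part of any chance baseline difference between arms passes into the estimated effect. A slope below 1 is likely for two reasons. TcPO2 is measured with error. And if eligibility rests on the week -1 reading, the week-0 value is subject to regression to the mean. With about 45 evaluable participants, neither the precision nor the imbalance is negligible in principle.

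The second is wording. Primary outcomes fixes the time point at 6 months, while the analysis section refers to the last observation. For anyone with a week-24 value the two agree. For a participant seen at week 12 but not at week 24, a literal reading of the analysis section could put a 3-month TcPO2 into the 6-month effect, while Primary outcomes would give that participant no value.

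**Working it through.** **Inputs from the protocol.** SD 5 mmHg, 10% dropout, N = 50 at 1:1, 90% power, α = 0.05. Evaluable per arm: 25 × 0.9 = 22.5.

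**Assumptions.** The SD of 5 is the SD of change, and the test is two-sided. The baseline SD (s0) and the slope (b) are not in the protocol; s0 = 5 is used below, with b varied.

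**1. Reproducing the stated sample size.** By the normal approximation, n per arm = 2 × 5² × (1.960 + 1.282)² / δ². At δ = 5.0 this is 21.0, rounded up to 22 per arm; 44 / 0.9 = 48.9, so 49 in total, against the stated 50. With the noncentral t it is 23 per arm, 46 in total, or 52 after dropout. The stated N therefore fits an unadjusted comparison of change with a difference near 5 mmHg. At δ = 3.95 (10% of 39.5, the middle of the entry window) the same formula gives 34 per arm, or 76 in total after dropout. The calculations below use δ = 5.0 because it is the value consistent with the protocol's own power.

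**2. Power of the planned t-test.** Standard error = 5 × √(2/22.5) = 1.49; noncentrality = 5.0 / 1.49 = 3.35; df = 43. Power = 90.6%.

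**3. Power of ANCOVA with the change SD held at 5.** Writing week-24 = a + b × baseline + residual, the change has variance s0²(1 − b)² + residual variance. So residual variance = 25 − s0²(1 − b)², with df = 42.

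| Slope b | Residual variance (s0 = 5) | Reduction | Power at 5.0 mmHg |
|---|---|---|---|
| t-test | 25.00 | – | 90.6% |
| 0.5 | 18.75 | 25% | 96.6% |
| 0.7 | 22.75 | 9% | 93.0% |
| 0.8 | 24.00 | 4% | 91.7% |
| 0.9 | 24.75 | 1% | 90.9% |
| 1.0 | 25.00 | 0% | 90.6% |

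The formula ignores the small cost of estimating the slope. A simulation with 22 and 23 per arm (200,000 trials) includes it. At b = 0.5, ANCOVA had 96.2% power against 90.5% for the t-test. At b = 1 it had 90.0% against 90.7%, a loss of under 1 point. Type I error was 0.050 for both methods.

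**4. Sensitivity to baseline SD, at 5.0 mmHg.** At b = 0.5, power is 94.7% for s0 = 4 and 97.5% for s0 = 5.48, the SD of a uniform distribution over the window (19/√12). At b = 0.7 it is 92.2% and 93.4%. With s0 = 3 and b = 0.7, the variance falls by only 9 × 0.09 / 25 = 3%.

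**5. Chance imbalance.** With s0 = 5, the baseline difference between arms has standard error 5 × √(2/22.5) = 1.49 mmHg. An imbalance of that size moves the change-score estimate by (1 − b) × 1.49: 0.75 mmHg at b = 0.5 (15% of 5.0), and 0.15 mmHg at b = 0.9.

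**6. The two definitions of change.** For participants with a week-24 value, the last observation of the 24-week trial is the end-of-trial value, and nothing changes. They diverge only where week 24 is missing and week 12 is present. The protocol does not say how many such participants to expect, so no figure is given for this point.

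**The case against.** The strongest reply is that the plan is coherent: the outcome is a change, the trial is sized on a change, and a change is tested. The estimate is unbiased over randomisation, and its standard error already includes chance baseline differences. At the difference that fits the stated N, the 90% target is met without adjustment. All of that stands, so the point is efficiency. It is also true that the gain could be negligible, since at slope 0.9 it is 0.3 of a power point. What remains is the asymmetry: several points of power if the slope is moderate, about 1 point or less lost if it is 1, from data already scheduled. Nor is the matter simply left to an SAP, because the protocol itself names the test.

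Several stronger readings are tempting but not supported:

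- A reader might infer that the t-test is biased or inflates type I error. It does neither.
- A reader might start from 73.6% power, the t-test figure at 3.95 mmHg. That shortfall comes from the 10% difference having no stated mmHg value, which is a separate issue.
- A reader might argue that an entry criterion with a "value of the foot ranged between 49 and 30 mmHg" lowers the slope by itself. Restricting the range of a baseline does not lower the slope on that same baseline. In a simulated example it was 0.69 with or without the window, and fell to 0.58 only when selection used a separate earlier reading. Taking the lowest of several sites is likewise not shown to lower it.
- A reader might see the repeated-measures ANOVA as a rival primary analysis. The protocol's wording marks it as additional.
- A reader might call the start undefined because TcPO2 is also taken at week -1. The visit table starts the intervention at week 0 and labels week -1 as screening.
- A reader might infer a carry-forward rule. None is stated. The sentence on change is generic, and the definition in Primary outcomes is specific to TcPO2 and can reasonably be taken to govern. Nor does the wording call for extension values, since the 18-month follow-up is set aside for additional analyses.

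**Conclusion.** The point holds as a free improvement. The planned comparison is valid but makes less use of the week-0 TcPO2 than it could. Under the assumptions above (change SD 5, baseline SD 5, 22.5 per arm, a 5.0 mmHg difference), the gain runs from about 6 power points at slope 0.5 to almost none at 0.9, and no single figure can be claimed because the protocol supplies neither slope nor baseline SD. The wording difference is real but minor. It concerns only participants without a week-24 value, and it calls for reconciliation of the two sections; it is not evidence of a faulty missing-data rule.

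**What to change.** In Planned statistical analysis, make the primary analysis of the continuous co-primary outcome an ANCOVA of week-24 TcPO2 on treatment and week-0 TcPO2. Keep the two-sample t-test on change and the repeated-measures ANOVA as supportive. For TcPO2, replace the last observation with week 24 and the start with week 0, in both sentences that describe change, so that they match Primary outcomes. How a missing week-24 value is handled can stay with the SAP; it should not be settled by this phrase.

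The change is confined to TcPO2. Extending it to every continuous outcome is not supported here, because the analysis section anticipates non-normal variables.

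Cost: one degree of freedom, a few words and no new data. If the slope is near 1 there is little or no gain, and a loss of about 1 power point or less.

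### The responder co-primary is tested without adjusting for baseline TcPO₂: a valid analysis, but one that may give up power that is cheap to recover

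*Protocol*

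**What the plan says.** Under Primary outcomes, the protocol names two co-primaries: peripheral perfusion (change in TcPO₂) and "the proportion of individuals who reaches a 10% increase of the TcPO₂ value from the baseline in each group". Under Planned statistical analysis, the χ² test "will be used for comparing proportions of participants in the 2 groups who reached the primary endpoint after the intervention". The effect measure is an RR with 95% CI that "will be calculated to demonstrate the relationship between the intervention and the achievement of the primary endpoint". No covariate, stratum or regression model is attached to this outcome. The repeated-measures analysis of variance in the same section does not address the proportion.

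Under Study population, entry requires a "TcPO₂ value of the foot ranged between 49 and 30 mmHg". The time schedule has TcPO₂ measured at screening (week -1), week 0, week 12 and week 24. The sample size paragraph (SD 5 mmHg, 10% dropout, 50 participants, 90% power) is based on the change in TcPO₂ only.

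**The concern.** The response threshold is a fraction of each participant's own baseline, so the rise needed differs between participants: 0.10 × 30 = 3.0 mmHg at one end of the entry range and 0.10 × 49 = 4.9 mmHg at the other. If TcPO₂ also regresses toward the mean, participants with low baselines tend to rise and those with high baselines to fall, which acts in the same direction. Regression to the mean is plausible here because entry is restricted to a TcPO₂ window and the lowest value of each participant is the one analysed.

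Baseline TcPO₂ is then prognostic for response, and a 2×2 table ignores it. At stake is power on a co-primary for which the protocol makes no power statement. There is also some extra variability in the RR when the arms differ by chance at entry.

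**Working it through.** **Inputs.** From the protocol: SD of change 5 mmHg, 50 participants 1:1, 10% dropout, α 0.05 (taken as two-sided), entry range 30 to 49 mmHg, response if the change is at least 0.10 × baseline. Assumed, because the protocol does not give them: baseline uniform over 30 to 49 mmHg, a constant treatment effect, and slope s of week-24 on baseline TcPO₂.

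**1. The protocol's own sample size.** n per arm = 2 × SD² × (1.960 + 1.282)² / δ². With δ = 5 mmHg: 2 × 25 × 10.51 / 25 = 21.0, rounded up to 22 per arm. Then 44 / 0.9 = 48.9, or 49 in total, which agrees with 50. With δ = 4.9 the result is the same. With δ = 3.95 (10% of the mid-range 39.5) it is 34 per arm and 76 in total. The stated size therefore fits an effect of about 5 mmHg, with about 22 evaluable per arm. The calculations below use these figures.

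**2. Threshold effect alone (s = 1).** P(response) = 1 − Φ((0.10 × baseline − effect) / 5).
- Control, baseline 30: 1 − Φ(0.60) = 0.274; baseline 49: 1 − Φ(0.98) = 0.164.
- Treated (5 mmHg), baseline 30: 1 − Φ(−0.40) = 0.655; baseline 49: 1 − Φ(−0.02) = 0.508.

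Baseline is prognostic, but not strongly. At mid-range the proportions are 0.215 and 0.583, and the usual two-proportion formula gives χ² power of 0.72 with 22 per arm.

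**3. Adding regression to the mean.** Let change = effect × arm + (s − 1)(baseline − 39.5) + error, with the error SD set so that the SD of change within arm stays 5. Response then means effect × arm + error ≥ 0.10 × baseline + (1 − s)(baseline − 39.5). The coefficient of baseline on the right is 0.10 + (1 − s). The threshold contributes only 0.10 of it; the rest is regression to the mean.

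The uniform baseline has variance 19² / 12 = 30.08. The share of the underlying variance explained by baseline is (1.1 − s)² × 30.08 divided by itself plus the error variance 25 − (1 − s)² × 30.08:
- s = 1.0: 0.30 / 25.30 = 1%
- s = 0.8: 2.71 / 26.50 = 10%
- s = 0.6: 7.52 / 27.71 = 27%
- s = 0.5: 10.83 / 28.31 = 38%

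**4. Power by simulation.** 22 per arm, effect 5 mmHg, 4,000 runs per scenario; Pearson χ² against the logistic score test for arm given baseline.

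| s | χ² | Adjusted | Gain (points) |
|---|---|---|---|
| 1.0 | 0.71 | 0.72 | 1 |
| 0.8 | 0.69 | 0.73 | 4 |
| 0.6 | 0.68 | 0.76 | 8 |
| 0.5 | 0.65 | 0.79 | 14 |

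The Monte Carlo standard error of each power is about √(0.7 × 0.3 / 4,000) = 0.7 points. Repeat runs with 44 or 45 evaluable gave gains of 0 to 2 points at s = 1.0, 1 to 4 at 0.8, about 8 at 0.6 and 12 to 14 at 0.5. For a 4 mmHg effect with 45 evaluable, power was 0.48 against 0.59 at s = 0.5 and 0.50 against 0.57 at s = 0.6.

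**5. Narrower baselines.** With a baseline SD of 3.5 instead of √30.08 = 5.5 and s = 0.6, power is 0.71 against 0.75, a gain of 4 points instead of 8.

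**6. Test level.** Under no effect, the χ² test rejected in 4.5 to 6.0% of runs. The adjusted score test rejected in 5.0 to 6.2%, with one run at 6.6% in which the χ² test itself stood at 6.0%.

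**7. Chance imbalance.** The between-arm difference in mean baseline has SD 5.5 × √(2/22) ≈ 1.6 mmHg. At s = 0.5 to 0.6, each 1 mmHg moved the responder risk difference by about 3 to 4 percentage points, so one SD of imbalance moves it by about 5 to 6 points.

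**The case against.** The strongest reply is that nothing here is wrong. The χ² test holds its level under 1:1 randomisation, and the planned confidence interval already reflects chance imbalance in entry TcPO₂. This stands. A reader might infer from the scaled threshold that the planned RR is biased, or that baseline matters so much by construction that a large power loss is certain. The documents support neither: the scaled threshold alone is worth 0 to 2 points, close to simulation error.

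The material gains come from a slope that the protocol does not state, and from an assumed baseline spread. A reader might also take at least 5 points as guaranteed once the slope is 0.6 or lower; step 5 shows that a narrower spread breaks this.

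Which measurement is the baseline also matters. The protocol speaks only of baseline and the value at the start, and TcPO₂ is taken at both week -1 and week 0, so week 0 is an inference. Under a model of a stable true value plus measurement error, gains are about 2 to 4 points if the value used for eligibility is itself the baseline (slopes about 0.74 to 0.94). They are about 7 to 8 points if eligibility uses week -1 and a separate week-0 value is the baseline; those baselines can then leave 30 to 49 mmHg.

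Adjustment also does not repair the missing power statement for this outcome: adjusted power is still about 0.72 to 0.79 for 5 mmHg. Finally, covariates are often left to an analysis plan, and none is shown here. That carries less weight, because the protocol itself names the test and the effect measure.

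**Conclusion.** The point holds as one of efficiency. The protocol fixes an unadjusted χ² test and crude RR for a co-primary defined relative to each participant's baseline, while a likely prognostic pre-treatment measurement is already collected. With 22 per arm and a 5 mmHg effect, the cost is about 0 to 2 points of power from the threshold alone and about 1 to 14 points if the week-24-on-baseline slope lies between 0.8 and 0.5. These figures assume an SD of change of 5 mmHg (the protocol's figure if that SD refers to change) and baselines uniform over 30 to 49 mmHg; a narrower spread lowers them. In none of the scenarios run did adjustment have lower power than the planned test, allowing for simulation error. The point does not show a biased estimate, an invalid test or a certain loss. It is a worthwhile, low-cost improvement.

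**What to change.** Under Planned statistical analysis, make the primary analysis of the responder co-primary a logistic model of response on arm and continuous baseline TcPO₂, with a score test for arm. State which pre-treatment measurement is the baseline, and use that same value both to define response and as the covariate. Report a marginal RR standardised over the baseline distribution, with a 95% CI by a named method such as the bootstrap or the delta method. Keep the crude 2×2 table and RR as a supplement.

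The cost is a short addition to the text and some extra programming, with no new data. The RR becomes model-based and can no longer be checked by hand, and the test level may reach about 6% at this sample size. Only the test was simulated, so the coverage of the chosen interval at about 22 per arm should be checked before it is fixed.

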Assessment of Female Sexual Function – Female sexual function will be studied through the FSFI questionnaire which assesses sexual activity over the past 4 weeks and includes 19 questions. The questionnaire will investigate six distinct domains (sexual desire, arousal, lubrication, orgasm, satisfaction and pain), and provide a total score indicative of global sexual function. A total FSFI score < 26.55 will be used to classify the presence of female sexual dysfunction. The FSFI questionnaire will be administered at visit 2 (week 0) and at the end of the study (week 24).

Evaluation of TcPO₂ - The measurement of transcutaneous oxygen tension will be performed on both limbs of each participant. Anterior tibial artery perfusion will be assessed near the base of the third finger, while posterior tibial artery perfusion will be evaluated near the lateral malleolus. The patients will be examined in supine position, after 20 minutes of rest. The application of the electrodes has to avoid areas with bony prominences, superficial veins or skin lesions. Measurement sites will be cleaned with an alcoholic solution, the electrodes will be fixed to the skin through an adhesive ring, after the application of a contact solution. Before each measurement, the oximeter will be calibrated for at least 10 minutes. The TcPO₂ measurement will be recorded for 16 minutes. According to manufacturer sheet, TcPO₂ value ≥ 50 mmHg is considered as indicator of a normal perfusion, while TcPO₂ value < 30 mmHg is referred to critical ischemia. The lowest value of each participant will be considered for the follow-up and the analysis.

Planned statistical analysis

The sample size calculation was performed based on the change of the primary endpoint (change in $TcPO_2$). Assuming an estimated standard deviation of 5 mmHg, a dropout rate of 10%, we expect to require at least 50 participants (in a 1:1 ratio LIRA:Control strategies) to achieve the 90% power to detect an 10% difference between group at a α -level of 0.05.

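### TcPO₂ change is tested by a t-test and again by a repeated-measures ANOVA with Scheffé, with neither ranked and the ANOVA not targeting the 6-month change

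*Protocol*

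**What the plan says.** Under Primary outcomes, the protocol states: "The co-primary outcomes of the study are the peripheral perfusion assessed at baseline and at the end of the study", together with the proportion reaching a 10% rise in TcPO₂. The between-arm change in TcPO₂ "will be calculated after 6 months", as the end-of-trial value minus baseline.

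Under Planned statistical analysis, "Δ values will be calculated as value at the last observation minus value at the start", and "Two-sample t-test will be used to compare differences between interventions". The responder co-primary has its own chi-square test and relative risk, which are not at issue here. The section then adds: "Data were also analyzed by analysis of variance for repeated measures with a post-hoc comparisons made with the Scheffé's test". One rule covers everything: "P value < 0.05 will be considered statistically significant".

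The ANOVA sentence names no outcome, does not say which effect is read (arm, visit or their interaction), does not say what Scheffé compares, and does not call the analysis supportive. The time schedule marks TcPO₂ at screening and at weeks 0, 12 and 24.

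**The concern.** Nothing exempts TcPO₂ from the ANOVA sentence, so the change co-primary receives at least two between-arm P values at the same threshold. They can disagree, because the ANOVA also uses week 12. A free choice between them raises the false-positive rate above 5%.

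The second analysis also answers a different question. The defined contrast is one number: the arm difference in change from baseline to 6 months. The ANOVA arm effect averages over visits, including week 0, before treatment can act. The interaction asks whether the arm difference varies anywhere across three visits. A Scheffé adjustment guards against searching over many contrasts, and only one was planned.

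**Working it through.** **Inputs.** From the protocol: two arms 1:1, N = 50, SD 5 mmHg, 10% dropout, 90% power, α 0.05, eligible TcPO₂ 30 to 49 mmHg. Assumed here: two-sided testing; the 10% difference read as 4.9 to 5 mmHg (10% of the top of the eligible range); 5 mmHg as the SD of change; compound symmetry with correlation ρ between visits; no missing data.

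**1. The plan's own figure.** For two means, n per arm = 2(1.960 + 1.282)² × 5² / δ².

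- δ = 4.9: 2 × 10.51 × 25 / 24.01 = 21.9, so 22 per arm and 44 in total. 44 / 0.9 gives 49, or 50 if each arm is rounded up.
- δ = 3.95 (middle of the eligible range): 34 per arm, 76 in total after dropout.

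So N = 50 reproduces at 4.9 to 5 mmHg from a two-group comparison of means, which matches the t-test and not the ANOVA.

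**2. What the ANOVA arm effect estimates.** With an effect of 0 at week 0, W at week 12 and E at week 24, it targets (0 + W + E)/3. For E = 4.95 mmHg this is 2.48 mmHg if W is half of E, and 3.30 mmHg if W equals E. Neither is the 6-month change.

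**3. Scheffé critical values,** √(k × F(0.95; k, df)), with 50 × 0.9 = 45 completers split 22 and 23:

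- Between two arms, k = 1, df = 43: 2.017, the ordinary t value.
- Over the 2-df interaction space, k = 2, df = 2 × 43 = 86: 2.49, against 1.99 for one planned contrast.

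**4. Power on the week-24 contrast,** effect 4.95 mmHg. The standard error is 5 × √(1/22 + 1/23) = 1.49, so the standardised effect is 4.95 / 1.49 = 3.32. The t-test has about Φ(3.32 − 2.017), or 90%. With Scheffé it is about Φ(3.32 − 2.49), or 79 to 80% by this approximation and 79% by simulation.

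**5. Two tests, no true effect** (simulation, 22 per arm, 20,000 trials per row):

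| ρ | t-test | interaction | they disagree | either | either, or arm effect |
|---|---|---|---|---|---|
| 0.3 | 5.36% | 5.26% | 5.26% | 7.94% | 12.84% |
| 0.5 | 5.00% | 4.97% | 5.12% | 7.54% | 11.92% |
| 0.7 | 5.01% | 5.03% | 5.10% | 7.57% | 12.29% |
| 0.9 | 4.87% | 5.07% | 4.86% | 7.40% | 11.87% |

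Check at ρ = 0.5: either = (5.00 + 4.97 + 5.12)/2 = 7.5%.

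**6. Two tests, true effect.** At 5 mmHg the t-test and interaction test disagree in about 7 to 8% of trials; at 3.95 mmHg, in about 13%.

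**7. Gain from baseline adjustment.** The variance of the week-24 difference adjusted for week 0, relative to that of the change score, is (1 + ρ)/2: 0.65 at ρ = 0.3 and 0.90 at ρ = 0.8. In simulation at 4.95 mmHg, power rose from about 90% to 98% and 92% respectively.

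**The case against.** The strongest reply is that the plan is readable as it stands. Change is defined at 6 months, the trial is sized on a two-group comparison of means, the t-test follows directly from the definition of Δ, and the ANOVA is introduced as an addition. On that reading the t-test decides and the ANOVA supplements it, and a formal hierarchy may sit in an analysis plan not shown. This is a fair inference, but the protocol never states it: it puts both analyses under one significance rule and ranks neither.

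Three stronger readings are tempting and are not supported.

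- A reader might infer that repeated-measures ANOVA is the wrong method. It is usable for two arms with repeated visits, and its interaction test held about 5% in the simulation. Scheffé across three visits is valid and only slightly stricter than Bonferroni (2.492 against 2.443, with 22 per arm).
- A reader might infer that the two analyses contradict each other. The documents show only that they can differ. They agree in about 92% or more of simulated trials under the null or at 5 mmHg, and give the same P value for variables measured only at weeks 0 and 24.
- A reader might infer that they necessarily run on different participants, since Δ goes to the last observation while classical ANOVA software drops incomplete cases. The protocol does not state listwise deletion, and Primary outcomes fixes TcPO₂ change at the end of the trial. On that basis someone lost before week 24 may leave both analyses.

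It is also true that the error inflation arises only if someone may claim whichever test succeeds. The protocol does not propose that; it leaves it open.

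**Conclusion.** The point holds in a limited form. The TcPO₂-change co-primary has a t-test and an unranked ANOVA at the same threshold, and the ANOVA effects are not the 6-month contrast. Scheffé adds nothing between two arms and is needlessly conservative on the week-24 contrast.

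The cost is a false-positive rate of about 7.5% instead of 5% if the t-test or the interaction test may be claimed, and about 12% if the ANOVA arm effect counts too. Power is about 79% instead of 90% if a Scheffé-adjusted week-24 contrast were the one used. The error rates rest on compound symmetry and complete data; the power figures also rest on a 4.95 mmHg effect and an SD of change of 5 mmHg. The protocol gives its effect only as a percentage.

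**What to change.** For TcPO₂ change, replace both the two-sample t-test and the ANOVA/Scheffé sentence with one deciding analysis: a mixed model for repeated measures on TcPO₂ at weeks 12 and 24, with arm, visit, arm-by-visit and week-0 TcPO₂. Include everyone with at least one post-baseline reading. State that the week-24 arm difference, with its 95% CI, is the only test of this co-primary. Delete Scheffé, and label any t-test or ANOVA of TcPO₂ that remains as supportive. Both sentences need changing: removing only the ANOVA would leave the t-test beside the new model, again with two unranked analyses.

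The cost is a few lines of text and one spare P value. All the data needed are already scheduled.
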